7.1.11. Imputation Rules for Partial or Missing Dates

For purposes of data listings, dates will reflect only the information provided by the investigator on the eCRF.

If start dates for adverse events or concomitant medications are completely missing, a worst case approach will be taken whereby the events will be considered treatment-emergent and the medications will be considered concomitant. If only partial information is available (e.g., only a month and year or only a year) and the partial information provides sufficient information to indicate the dates are prior to the start of study treatment (e.g., month/year less than month/year of first dose) then these will be considered to have started prior to treatment; otherwise a similar worst case approach will apply and these will be considered to have started after treatment.

Death Date

Missing or partial death dates will be imputed based on the last contact date:

- If the date is completely missing, it will be imputed as the day after last contact date ([Section 7.1.2](#)).
 - If the day or month is missing, death will be imputed to the maximum of the full (non-imputed) day after the date of last contact and the following:
 - Missing day: 1st day of the month and year of death, or
 - Missing day and month: January 1st of the year of death.

Exposure Date

No imputation will be done for first dose date. Date of last dose of study drugs, if unknown or partially unknown, will be imputed as follows:

- If the last date of study drugs is completely missing and there is no End of Treatment eCRF page and no death date, the participant should be considered ongoing and use the cutoff date for the analysis as the last dosing date. Note: the study team should confirm that the participant is actively receiving dose at the time of the data cutoff.
- If the last date of study drugs is completely or partially missing and there is EITHER an End of Treatment eCRF page OR a death date available (within the data cutoff date), then impute this date as the last dose date:
 - = 31DECYYYY, if only Year is available and Year < Year of min (EOT date, death date)
 - = Last day of the month, if both Year and Month are available and Year = Year of min (EOT date, death date) and Month < Month of min (EOT date, death date)
 - = min (EOT date, death date), for all other cases.

Date of Start of New Anticancer Therapy

Incomplete dates for start date of new anticancer therapy will be imputed as follows and will be used for determining censoring dates for efficacy analyses. PD date below refers to PD date by investigator assessment. If the imputation results in an end date prior to the imputed start date, then the imputed start date should be set to the end date.

- The end date of new anticancer therapy will be included in the imputations for start date of new anticancer therapy. If the end date of new anticancer therapy is
 - Completely missing, then it will be ignored in the imputations below
 - Partially missing with only year (YYYY) available, then the imputations below will consider 31DECYYYY as the end date of the new anticancer therapy
 - Partially missing with only month and year available, then the imputations below will consider the last day of the month for MMMYYYY as the end date of the new anticancer therapy
- For participants who have not discontinued study treatment at the analysis cut-off date, last dose of study treatment is set to the analysis cut-off date in the imputations below.
- If the start date of new anticancer therapy is completely or partially missing, then the imputed start date of new anticancer therapy is derived as follows:
 - Start date of new anticancer therapy is completely missing

Imputed start date = min [max(PD date + 1, last dose of study treatment + 1), end date of new anticancer therapy]

- Only year (YYYY) for start of anti-cancer therapy is available

IF YYYY < Year of min [max(PD date + 1, last dose of study treatment + 1), end date of new anticancer therapy] THEN imputed start date = 31DECYYYY;

ELSE IF YYYY = Year of min [max(PD date + 1, last dose of study treatment + 1), end date of new anticancer therapy]

THEN imputed start date = min [max(PD date + 1, last dose of study treatment + 1), end date of new anticancer therapy]

ELSE IF YYYY > Year of min [max(PD date + 1, last dose of study treatment + 1), end date of new anticancer therapy]

THEN imputed start date = 01JANYYYYY

- Both Year (YYYY) and Month (MMM) for start of anticancer therapy are available

IF

YYYY = Year of min [max(PD date + 1, last dose of study treatment + 1), end date of new anticancer therapy], AND

MMM < Month of min [max(PD date + 1 day, last dose of study treatment + 1 day), end date of new anticancer therapy]

THEN

imputed start date = DAY (Last day of MMM) MMM YYYY ;

ELSE IF

YYYY = Year of min [max(PD date + 1, last dose of study treatment + 1), end date of new anticancer therapy], AND

MMM = Month of min [max(PD date + 1 day, last dose of study treatment + 1 day), end date of new anticancer therapy]

THEN

imputed start date = min [max(PD date + 1 day, last dose of study treatment + 1 day), end date of new anticancer therapy];

ELSE IF

YYYY = Year of min [max(PD date + 1, last dose of study treatment + 1), end date of new anticancer therapy], AND

MMM > Month of min [max(PD date + 1 day, last dose of study treatment + 1 day), end date of new anticancer therapy]

THEN

imputed start date = 01 MMM YYYY;

ELSE IF

YYYY < Year of min [max(PD date + 1, last dose of study treatment + 1), end date of new anticancer therapy]

THEN

imputed start date = DAY (Last day of MMM) MMM YYYY;

ELSE IF

YYYY > Year of min [max(PD date + 1, last dose of study treatment + 1), end date of new anticancer therapy]

THEN

imputed start date = 01 MMM YYYY.

AE Dates

- AE Onset Date:

If completely missing, the onset date will be set to first dose date if the first dose date is less than AE stop date. Otherwise if the first dose date is after AE stop date, then set the onset date to the earliest of non-missing AE stop date or informed consent date.

- AE Stop Date:

If completely missing, the stop date will be imputed as the latest of the end of study date, death date, last dose date of the study treatment, or onset date.

- Partial AE Date:

Partial AE date will be imputed based on the imputation rule for “Other Missing or Partial Dates”. If the AE onset date is imputed from a partial AE date and the first dose date falls in the same month as the AE onset date, the following will be done:

- The AE onset date is reset to the first dose date.
- If AE stop date is imputed, and less than the first dose date, set the AE stop date to the first dose date.

Other Missing or Partial Dates

Imputation methods for other partial dates as follows:

- If the day of the month is missing for a start date used in a calculation, the first day of the month will be used to replace the missing date.
- If both the day and month are missing for a start date, the first day of the year is used.
- For stop dates, the last day of the month, or last day of the year is used if the day or day and month are missing, respectively.

These rules are used unless the calculations result in negative time durations (e.g., date of resolution cannot be prior to date of onset). In these cases, the resolution and onset dates will be the same and the duration will be set to 1 day.

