7.1.4. On-treatment Period

On-treatment period is defined as the time from the first dose date of study treatment to the last dose of study drug administration date (when both drugs are permanently discontinued) + 30 days or the earliest date of subsequent anti-cancer drug therapy minus 1 day, whichever occurs first.

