7.6.1. Extent of Study Drug Exposure

Duration of exposure will be evaluated separately for encorafenib and binimetinib. It is defined as (date of last (non-zero) dose of study drug – date of first dose of study drug) + 1 and will be summarized in months including descriptive statistics (n, mean, standard deviation, median, minimum, maximum) and a frequency distribution (≤ 1 month, >1 to ≤ 3 months, > 3 to ≤ 6 months, >6 to ≤ 12 months, >12 to ≤ 24 months, > 24 months).

Cumulative dose is defined as:

- **Actual cumulative dose** (mg) = sum of all actual doses taken during the dosing period

For participants who did not take any drug the actual cumulative dose is by definition equal to zero.

Dose intensity and relative dose intensity are defined as follows:

- **Actual dose intensity** (mg/day) = actual cumulative dose (mg) / [duration of exposure (days)]
- **Relative dose intensity** = $100 \times [\text{actual dose intensity (mg/day)} / \text{intended dose intensity (mg/day)}]$

A summary of exposure, including duration, cumulative dose, actual dose intensity, and relative dose intensity (including categories $<50\%$, $50\%<75\%$, $75\%<90\%$, $90\%<110\%$, and $\geq 110\%$, if applicable), will be presented for each study drug. Duration of exposure, cumulative dose, actual dose intensity, and relative dose intensity will also be listed for each participant.

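### SAP 7.1.11 imputes a last-dose date later than the recorded month allows when that month falls in the calendar year before end of treatment or death

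*SAP*

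**What the plan says.** SAP 7.1.11, under Exposure Date, covers a last-dose date that is partly or wholly missing when an EOT page or a death date exists. Call the earlier of the EOT and death dates the reference date. There are three branches:

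1. Year only, in an earlier year: "31DECYYYY, if only Year is available and Year < Year of min (EOT date, death date".
2. Year and month known: "Last day of the month, if both Year and Month are available and Year = Year of min (EOT date, death date". A second condition is that the recorded month precedes the reference month. The result is the last day of the recorded month.
3. Otherwise: "min (EOT date, death date), for all other cases".

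The rule for a partial start date of new anticancer therapy, later in the same section, has a separate branch for year and month known with the year before its own reference year. Its result is "imputed start date = DAY (Last day of MMM) MMM YYYY".

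The imputed date is used in several places. SAP 7.6.1 measures duration of exposure to the "date of last (non-zero) dose of study drug". In SAP 7.1.4 the relevant wording is: "On-treatment period is defined as the time from the first dose date of study treatment to the last dose of study drug administration date". To that date it adds 30 days once both drugs have been stopped for good, but the period ends the day before subsequent anticancer drug therapy if that comes sooner. SAP 7.6.4 defines treatment-emergent adverse events by that period. SAP 7.6.4 also splits deaths at 30 days after last dose.

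**The concern.** A known month in an earlier year satisfies neither of the first two branches. Branch 1 needs the month to be missing, and branch 2 needs the years to match. The record drops to branch 3, which replaces it with a date in a later calendar year than the one the site entered.

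Two features point to an oversight. The neighbouring rule for new anticancer therapy includes the missing branch. The outcome is also inverted: entering only the year gives 31 December of that year, while entering the month as well gives a later date that contradicts the entry.

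At stake are derived safety quantities: exposure duration, dose intensity, the treatment-emergent window and the 30-day split of deaths. An affected record can bring events after treatment into on-treatment tables.

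**Working it through.** The plan states no figure here, so the check is to apply the branches literally to example dates. All dates are illustrative. The inputs are the three branches of SAP 7.1.11, the formulas in SAP 7.6.1 and 7.1.4, and the 42-consecutive-day limit on missed dosing in Protocol 6.6.1, which bounds a realistic gap between last dose and EOT.

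**Step 1: which branch applies**

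| Recorded last dose | Reference date | Branch | SAP result | Latest date the record allows | Excess |
|---|---|---|---|---|---|
| Nov 2020 | 15 Dec 2020 | 2 | 30 Nov 2020 | 30 Nov 2020 | 0 days |
| Jan 2021 | 15 Feb 2021 | 2 | 31 Jan 2021 | 31 Jan 2021 | 0 days |
| 2020 only | 11 Jan 2021 | 1 | 31 Dec 2020 | 31 Dec 2020 | 0 days |
| Dec 2020 | 5 Jan 2021 | 3 | 5 Jan 2021 | 31 Dec 2020 | 5 days |
| Nov 2020 | 11 Jan 2021 | 3 | 11 Jan 2021 | 30 Nov 2020 | 42 days |

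The first three rows behave properly; the last two do not. The direction is general: a reference date in a later year is on or after 1 January of that year, so it follows the last day of any month in the recorded year.

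**Step 2: exposure, for the last row**

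- 30 November to 11 January = 31 days of December + 11 = 42 days. This is a minimum, because the true last dose may be earlier in November.
- With an assumed first dose on 1 June 2020, duration = last dose − first dose + 1. It is 183 days to 30 November and 183 + 42 = 225 days to 11 January.

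**Step 3: dose intensity**

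Actual dose intensity = cumulative dose / duration of exposure. If cumulative dose is unchanged, the ratio of imputed to corrected intensity is 183 / 225 = 0.813. A relative dose intensity of 100% would show as 81.3%. If programming also credits doses for the imputed days, cumulative dose rises instead and the fall is smaller; the SAP does not say which applies.

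**Step 4: deaths within 30 days**

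Take a death on 15 January 2021. The reference date is still 11 January. Days after last dose under the SAP: 15 − 11 = 4, inside 30 days. From 30 November: 31 + 15 = 46 at least, outside 30 days.

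**Step 5: treatment-emergent window**

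- Uncapped end under the SAP: 11 January + 30 = 10 February 2021. From 30 November: 30 December 2020. The window is 42 days longer.
- If subsequent anticancer drug therapy starts on or before 31 December 2020, both versions end the day before it, and nothing changes.
- The window runs from when both drugs are stopped. If the other drug has a complete last-dose date on or after 11 January 2021, nothing changes either.

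**The case against.** The strongest case against the point is about reach. The gap matters only if two things coincide: last dose and reference date fall in different calendar years, and the day of last dose is missing while its month is known. The plan works against the second. Protocol 6.7 requires the last-dose date in the eCRF, Protocol 7.4.1 gives patients a diary with the date and time of every dose of both drugs, and Protocol 6.4 adds capsule and tablet counts and interviews. Interruptions are entered as zero-dose records (SAP 7.6.1.1). A reader might infer from self-administration and permitted dose holds that affected records will be common. The documents show only that last dose and EOT can straddle a new year, not that partial dates are usual. That objection stands.

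It can also be said that the record itself is untouched, because SAP 7.1.11 keeps listing dates as the investigator entered them, and that a longer window errs toward counting events, in the spirit of the worst-case approach in the same section. Both limit the harm. Neither justifies the rule: derived durations still go into summaries and listings, and the worst-case approach there concerns adverse event and medication start dates and itself gives way when partial information settles the question.

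The general stop-date convention at the end of SAP 7.1.11 would give the right answer, but it applies to other dates and does not override the specific last-dose rule.

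**Conclusion.** The rule is wrong as written for one pattern of partial date, and its effect is narrow. For every affected record, duration of exposure is overstated, by 5 days and at least 42 days in the two examples here. Dose intensity tends to be understated, because exposure is its denominator. A death may be counted as within 30 days of last dose when it was not.

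Three stronger readings should be resisted:

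- **That the treatment-emergent window always lengthens.** SAP 7.1.4 caps it at subsequent drug therapy and starts the 30 days only when both drugs have stopped, so some affected records keep the same window.
- **That overstatements well beyond 42 days follow from the permitted dose hold.** With a November record, a minimum excess above 42 days needs an EOT after 11 January, hence a delay that the hold alone does not explain.
- **That the primary result is at risk.** Response rate does not use last-dose date directly. It could be reached only through an imputed start of new anticancer therapy, which needs a second missing date in the same participant.

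The conclusion about the logic rests on the SAP text alone. The sizes rest on illustrative dates and, for exposure totals and dose intensity, an assumed first dose on 1 June 2020. The number of affected records is unknown.

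**What to change.** In SAP 7.1.11, Exposure Date, keep the result of the second branch and change its condition: it should apply whenever year and month are both recorded and that year and month, taken together, precede the year and month of the earlier of EOT and death. In programming terms: recorded year < reference year, or recorded year = reference year and recorded month < reference month. The other two branches stay as they are.

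This brings the rule into line with the earlier-year branch for new anticancer therapy and leaves every correctly handled date in the table above unchanged. The cost is one line of the SAP and one programming condition, with no extra data collection.

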7.6.4. Adverse Events

Treatment-emergent adverse events (TEAEs) are defined as AEs with onset date during the on-treatment period.

Unless otherwise stated, only TEAEs will be presented in summary tables. However, all AEs will be presented in listings. AEs and SAEs will be coded by PT and SOC using the latest available MedDRA version.

The severity of an AE will be assessed by the investigator using the NCI CTCAE, Version 4.03. For participants with more than 1 AE within a SOC or PT, only the highest grade will be included in by-severity summaries.

The investigator will also assess whether the AE is related to study drugs (i.e., a treatment-related AE). For participants with more than 1 AE within a SOC or PT, the highest level of relationship (related is higher than not related) will be included in the by relationship summaries. AEs will be considered treatment related if they are related to encorafenib and/or binimetinib.

For summaries by SOC and PT, each participant will be counted at most once per SOC and at most once per PT. For summaries by PT, each participant will be counted at most once per PT.

Overall summary of safety table will include numbers and percentages of the following:

- Participants with at least 1 TEAE regardless of causality
- Participants with at least 1 treatment-related TEAE
- Participants with Grade 3 or 4 TEAEs
- Participants with Grade 3 or 4 treatment-related TEAEs
- Participants with Grade 5 TEAEs
- Participants with Grade 5 treatment-related TEAEs
- Participants with at least 1 treatment-emergent SAE
- Participants with at least 1 treatment-related SAE
- Participants who discontinued study drug due to a TEAE regardless of causality
 - TEAE leading to encorafenib discontinuation
 - TEAE leading to binimetinib discontinuation
- Participants with a dose reduction due to a TEAE
 - TEAE requiring encorafenib dose reduction
 - TEAE requiring binimetinib dose reduction
- Participants with a dosing interruption due to a TEAE
 - TEAE requiring encorafenib dosing interruption
 - TEAE requiring binimetinib dosing interruption

All TEAE summaries will be displayed (frequency counts and percentages) alphabetically by system organ class (SOC) and preferred term (PT) by descending frequency within SOC

based on “Total” group, if not otherwise noted. Individual summary tables showing the incidence of participants with the following subsets of TEAEs will be generated:

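### SAP 7.1.11 gives two conflicting rules for an adverse event onset recorded only as the year of first dose, when first dose falls in February to December

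*SAP*

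**What the plan says.** SAP 7.1.11 (Imputation Rules for Partial or Missing Dates) deals with incomplete AE start dates in two places.

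The opening paragraph classifies events. It covers the year-only case by name: "If only partial information is available (e.g., only a month and year or only a year". The event counts as starting before treatment if "the partial information provides sufficient information to indicate the dates are prior to the start of study treatment"; "otherwise a similar worst case approach will apply and these will be considered to have started after treatment".

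The later AE Dates block assigns a calendar date. "Partial AE date will be imputed based on the imputation rule for" other missing or partial dates, and that general rule reads: "If both the day and month are missing for a start date, the first day of the year is used". One safeguard follows. For an onset imputed from a partial date, if "the first dose date falls in the same month as the AE onset date", then "The AE onset date is reset to the first dose date".

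SAP 7.6.4 says that TEAEs "are defined as AEs with onset date during the on-treatment period", and SAP 7.1.4 starts that period at the first dose date. Unless otherwise stated, the AE summary tables show TEAEs only, while listings show all AEs. SAP 7.6.4 also computes time to AE onset as AE start date minus first dose date plus 1, and tabulates it for treatment-emergent AEs of special interest (AESIs).

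**The concern.** A year-only onset in the year of first dose could fall on either side of first dose. The opening paragraph settles that doubt conservatively, by counting the event. The date rules settle it the other way for most start dates, because 1 January comes before first dose and the reset reaches only January starters. The SAP does not say whether the classification or the imputed date decides TEAE status.

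Two neighbouring rules in 7.1.11 suggest an omission, not a choice. An AE with no onset date at all is placed on the first dose date unless it stopped earlier, so knowing the year makes the handling less conservative. For new anticancer therapy, a year-only start in the same year as the reference date is set to that reference date and not to 1 January. The AE rule has no such same-year branch.

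The AE summary tables are at stake under one reading, and the AESI time-to-onset summaries under the other.

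**Working it through.** The documents state no figure on this point, so there is none to reproduce. The check applies both rules to the same records.

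**Inputs**
- Year-only start date becomes 1 January of the recorded year (SAP 7.1.11, Other Missing or Partial Dates).
- Partial AE dates use that rule, with the same-month reset (SAP 7.1.11, AE Dates). I read same month as the same month of the same year.
- Worst-case rule: before treatment only if the partial date shows it (SAP 7.1.11, opening paragraph).
- The on-treatment period starts at first dose (SAP 7.1.4); TEAE status follows onset date (SAP 7.6.4).

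**Formulas.** Let Y be the recorded AE year and F the first-dose date.
- Date rule: onset I = 1 January Y, replaced by F if F is in January of Y. The event is pre-treatment if I < F.
- Worst-case rule: the event is pre-treatment only if Y < year of F.

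**Results for year-only onsets, over every possible first-dose day in 2019, 2020 and 2021**

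| Recorded year against first-dose year | Date rule | Worst-case rule | Discordant first-dose days |
|---|---|---|---|
| Earlier | pre-treatment | pre-treatment | 0 |
| Same, first dose in January | onset reset to first dose | after treatment | 0 |
| Same, first dose February to December | pre-treatment | after treatment | all |
| Later | after first dose | after treatment | 0 |

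In the same-year case the rules disagree on 365 − 31 = 334 of 365 first-dose days (91.5%), or 366 − 31 = 335 of 366 in a leap year (91.5%).

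**Month-and-year dates.** For 366 first-dose days in 2020, 3 AE years and 12 AE months (366 × 3 × 12 = 13,176 combinations), none is discordant. The reset works there.

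**Example.** First dose is 15 June 2020 and onset is recorded as 2020. The imputed onset is 1 January 2020. June 15 is day 31 + 29 + 31 + 30 + 31 + 15 = 167 of that year.
- If the imputed date decides, the onset precedes the on-treatment period and the event is not a TEAE.
- If the worst-case rule decides, the event is a TEAE, and for an AESI the time to onset is 1 − 167 + 1 = −165 days. A first dose on 1 February (day 32) gives 1 − 32 + 1 = −30; one on 31 December of a 365-day year gives 1 − 365 + 1 = −363.

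SAP 7.6.4 takes the first occurrence when a participant has several episodes of an AE. On the second reading, the imputed date would therefore displace any dated on-treatment episode of that AE.

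**Plausibility of the imputed date.** Protocol 7.1.1 limits screening to 28 days. A first dose on 1 February puts consent no earlier than 4 January (28 days before), within a single screening period. AE collection starts at consent (protocol 7.5.1), so in every discordant case the imputed onset lies before the collection window.

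**The case against.** The strongest reply is that the two rules do different jobs. The opening paragraph decides whether an AE is treatment-emergent, and it names year-only dates. The later rules only supply a date for calculations, and the 1 January line sits in a generic list reached by cross-reference. On that reading no event leaves the TEAE tables. This is reasonable, and it means loss from the tables cannot be asserted as fact. But the SAP does not state it, 7.6.4 defines TEAEs by onset date, and the reading still leaves a negative time to onset.

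A second reply is that 7.1.11 ends with an override for negative durations. Its example is resolution before onset, and its remedy makes those two dates equal and sets the duration to 1 day. It does not move onset to first dose, so it does not repair this.

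A third reply is that few records can be affected. AEs are assessed continuously with visits each 28-day cycle, and SAP section 8 plans programmed edit checks. This stands. Deaths are also summarised separately from the Death eCRF page.

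A reader might infer that year-only AEs are generally dropped, or that about 92% of them are misclassified. The documents support neither. The 91.5% (11 of 12, or 92%, if counted in months) is a share of calendar time, not of events. Some of these AEs may truly precede first dose, so discordant between rules is the accurate term. Nor do the two harms add up: a given record is either missing from the TEAE tables or present with a negative onset time.

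**Conclusion.** The contradiction is real and confined to one case: only the year of onset is recorded, it is the year of first dose, and first dose falls in February to December. There the imputed onset always precedes first dose, while the worst-case rule counts the event as starting after treatment. Neither reading of the SAP gives a clean result.

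This is a minor point. The documents do not give the number of year-only AE onsets, so no effect on TEAE incidence can be calculated, and the primary endpoint is untouched. The conclusion assumes that the reset requires the same month of the same year, and that consent and first dose belong to one screening period where the collection window is used as supporting evidence.

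**What to change.** Keep the existing imputation rules and make two additions to SAP 7.1.11:

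1. In the AE Dates block, extend the reset to onsets with a missing month whose recorded year equals the first-dose year, and set onset to the first dose date. If the AE stop date is before first dose, handle the record as the existing rule does for a completely missing onset (the earlier of the non-missing stop date and the consent date).
2. State that the opening worst-case rule decides treatment-emergence, and that a stop date before first dose is enough to show that the event started earlier. Without that last clause, the two rules could disagree again for events that ended before treatment.

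Onsets clearly before or after the first-dose year keep their present handling. Where no earlier stop date applies, the discordant first-dose days fall from 334 of 365 (335 of 366 in a leap year) to 0.

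The cost is a sentence or two in the SAP and a small programming change before database lock. No new data are needed.
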